This sample size calculation reflects the use of a 90% performance goal as noted above in the hypothesis section and in the CIP. Again, this was done to ensure that there would be sufficient data to achieve the 80% performance goal when taking into account lost to follow up due to death, etc. The following

	PEPNS Study Statistical Analysis Plan <small>CONFIDENTIAL: THIS DOCUMENT AND ALL INFORMATION CONTAINED HEREIN IS PROPRIETARY TO STIMDIA MEDICAL, INC. AND IS NOT TO BE DISCLOSED WITHOUT THE EXPRESS WRITTEN PERMISSION OF STIMDIA MEDICAL, INC.</small>	Document Number SAP0001	Rev. Level 1
---	--	-----------------------------------	------------------------

assumptions were the basis for the sample size calculation for the performance endpoint evaluating stimulation capture of the diaphragm:

- Power: 80%
- 1-sided α : 0.025
- Performance goal: 90%
- Expected success rate: 97.5%

With an anticipated success rate of 97.5% and a performance goal of 90%, 80 observations would yield $\geq 80\%$ power. Note that, for the purposes of sample size calculations, the observations are assumed to be independent. However, the primary analyses will account for within patient correlation, as described below. Increasing the number of observations will increase the statistical power.

Methods:

The proportion of successful capture will be analyzed using a logistic regression model accounting for patient as a random effect. The null hypothesis will be tested comparing the lower bound of the 95% two-sided confidence interval for the estimated percent agreement to the performance goal of 80% (see note above). If the lower bound is greater than 80%, the null hypothesis will be rejected and the endpoint will be considered met.

If the logistic regression model does not converge (i.e. it does not provide reliable estimates of diaphragm capture), other methods will be used to characterize the capture rate. The method used will be dependent on the data and will be described in detail along with the reasons for using that method.

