An interim analysis of the primary endpoints may be done on the first 10 patients that were stimulated on both phrenic nerves. If they are met the secondary and other remaining analyses will also be performed. If not, the study will continue to enroll patients and all study endpoints and additional analyses will be analyzed when enrollment has been completed. If an interim analysis is done, the significance level used for testing will be 0.0125. At the final analysis (if needed) the significance level used for testing will be 0.0194. These levels were derived using a power cumulative error spending function with the parameter (rho) set to 1.0. This setting produces Pocock type boundaries (i.e. approximately equal spending for the two tests).

If an interim analysis is not done, the final analysis will use a significance level of 0.025 for testing the primary endpoints.

SECONDARY ENDPOINTS

The secondary endpoints are safety related and examine the percentage of patients who receive safe and successful placement of the multipolar lead in the left and right phrenic nerve utilizing ultrasound guidance and the percentage of patients who experience one or more serious device/procedure-related adverse events during the study.

- The percentage of patients who receive safe and successful placement of the multipolar lead in the left and right phrenic nerve utilizing ultrasound guidance will be determined.
- Phrenic nerve stimulation in synchrony with Mechanical Ventilation (MV) breaths will be measured to verify that it occurs with inspiration.
- The percentage of patients who experience one or more serious device/procedure-related adverse events during the study will be reported.

	PEPNS Study Statistical Analysis Plan	Document Number SAP0001	Rev. Level 1
<small>CONFIDENTIAL: THIS DOCUMENT AND ALL INFORMATION CONTAINED HEREIN IS PROPRIETARY TO STIMDIA MEDICAL, INC. AND IS NOT TO BE DISCLOSED WITHOUT THE EXPRESS WRITTEN PERMISSION OF STIMDIA MEDICAL, INC.</small>			

Safe and Successful Lead Placement

The percentage of patients who received safe and successful placement of the multipolar lead on the Left and right phrenic nerve utilizing ultrasound guidance will be evaluated in terms of the mean and standard deviation for preparation, placement, securement, removal and twitching. Twitching includes neck spasms, arm movement, shoulder movement on unwanted visible stimulation. This will be reviewed on a site basis, by neck circumference and BMI.

Adverse Events

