6. STATISTICAL METHODOLOGY

STATISTICAL PROCEDURES

The primary statistical methods used in this study will be descriptive where continuous variable will be summarized using means, medians, standard deviation, minimums and maximums and categorical variables will be summarized using frequencies and percent for each categorical level.

The primary endpoint will be analyzed using a logistic regression where diaphragm capture (yes/no) is the dependent variable and time point and subject are the independent fixed effect and random effect predictors. The point estimate of the diaphragm capture rate will be estimated from logistic regression model along with a two-sided 95% confidence interval. The lower bound of that confidence interval will be compared to the performance goal of 80%. If the lower bound is above 80%, then the endpoint will have been achieved.

Secondary endpoints will be summarized as noted in the secondary endpoints section. Each endpoint will be summarized descriptively.

Additional evaluations will also be summarized descriptively. In addition, diaphragm thickness over time will be modeled using regression analysis. The slope parameter and 95% confidence intervals will be presented. Additional diaphragm thickness analyses may be run.

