If an interim analysis is performed, the database will be temporarily locked at the time of the interim analysis and the clinical study report will include the date that the data was transferred from the database to the statistician for the interim analysis. It will also specify whether or not the data had been monitored. The secondary end points and other remaining interim analyses will only be performed if the primary endpoints were met. If not, the study will continue to enroll patients and all study endpoints and additional analyses will be analyzed when enrollment has been completed. At the interim analysis the significance level used for testing will be 0.0125 which translates into calculating a 98.75% two-sided confidence interval on the capture rate and comparing the lower bound to 80%. At the final analysis (if needed) the significance level used for testing will be 0.0194 which translates into calculating a 98.06% two-sided confidence interval on the capture rate and comparing the lower bound to 80%. These levels were derived using a power cumulative error spending function with the parameter (rho) set to 1.0. This setting produces Pocock type boundaries (i.e. approximately equal spending for the two tests).

	PEPNS Study Statistical Analysis Plan <small>CONFIDENTIAL: THIS DOCUMENT AND ALL INFORMATION CONTAINED HEREIN IS PROPRIETARY TO STIMDIA MEDICAL, INC. AND IS NOT TO BE DISCLOSED WITHOUT THE EXPRESS WRITTEN PERMISSION OF STIMDIA MEDICAL, INC.</small>	Document Number SAP0001	Rev. Level 1
---	--	-----------------------------------	------------------------

7. MEASURES TO ADJUST FOR MULTIPLICITY, CONFOUNDERS, HETEROGENEITY, ETC.

Since the study cohort was 9 Caucasian men and 1 Caucasian woman and study was very small no heterogeneity, multiplicity or confounder statistical analyses will be run. However, summary data may be presented for the different types of patients (neuro trauma, COPD etc.) to try and see if there were any trends or if therapy was more effective for one of the patient populations since this was one of the study objectives.

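### If the optional interim is done, the SAP's 98.75% and 98.06% intervals test at half the one-sided levels they are paired with, and 0.0194 does not follow from the stated spending function

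*SAP*

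**What the plan says.** **Without an interim.** SAP Section 2 (Primary Endpoints) lists a one-sided alpha of 0.025 and 80% power. The Methods paragraph tests the null hypothesis by "comparing the lower bound of the 95% two-sided confidence interval for the estimated percent agreement to the performance goal of 80" per cent. Section 6 repeats this: the capture rate is estimated "along with a two-sided 95% confidence interval" and the lower limit is compared with 80%. Section 2 also says: "If an interim analysis is not done, the final analysis will use a significance level of 0.025 for testing the primary endpoints".

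**With an interim.** Section 2 states: "An interim analysis of the primary endpoints may be done on the first 10 patients that were stimulated on both phrenic nerves". The interim level is 0.0125 and the final level 0.0194. On their origin: "These levels were derived using a power cumulative error spending function with the parameter (rho) set to 1.0". If the primary endpoints are not met at the interim: "If not, the study will continue to enroll patients". No futility boundary appears anywhere.

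**The intervals.** Section 6 adds the conversion. For the interim, "the significance level used for testing will be 0.0125 which translates into calculating a 98.75% two-sided confidence interval"; for the final analysis, "the significance level used for testing will be 0.0194 which translates into calculating a 98.06% two-sided confidence interval". Each lower limit is compared with 80%.

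**The concern.** There are two separate faults.

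First, the SAP pairs its one-sided 0.025 with a 95% two-sided interval, so a level *a* goes with an interval of coverage 1 − 2*a*. Section 6 switches to 1 − *a* for the interim and final levels. Level and interval are then two different rules for the same primary endpoint. They disagree when the one-sided p-value lies between 0.00625 and 0.0125 at the interim, or between 0.0097 and 0.0194 at the final analysis.

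Second, the final level of 0.0194 looks too large for a design that spends 0.0125 at the interim and stops only for success.

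The interim verdict decides whether the remaining analyses are run then or enrolment continues, so the choice of rule should not be left open until the data are seen. The branch is a live one. The interim set is the first 10 bilaterally stimulated patients, Table 3 of the SAP already lists ten patient IDs, and Sections 7 and 8 describe a cohort of 9 men and 1 woman.

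**Working it through.** **Inputs**

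| Quantity | Value | Source |
|---|---|---|
| Overall alpha | 0.025, one-sided | SAP 2, Sample Size |
| Power | 80% (beta 0.20) | SAP 2, Sample Size |
| Stated levels | 0.0125, then 0.0194 | SAP 2 and 6 |
| Stated intervals | 98.75%, then 98.06%, two-sided | SAP 6 |
| Spending function | power family, rho = 1 | SAP 2 and 6 |
| Interim rule | success only; otherwise enrol on | SAP 2 and 6 |
| Interim set | first 10 bilateral patients | SAP 2 |
| Maximum enrolment | 20 | Protocol 6 |
| First two patients | safety analysis only | SAP 2 |

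**Step 1: interval to level.** The lower limit of a two-sided interval of coverage 1 − *c* tests at one-sided *c*/2.

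- 95%: 0.05/2 = 0.025. This reproduces the SAP's no-interim rule.
- 98.75%: 0.0125/2 = 0.00625, not 0.0125.
- 98.06%: 0.0194/2 = 0.0097, not 0.0194.

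In the other direction, 0.0125 needs 1 − 2 × 0.0125 = 97.5%, and 0.0194 needs 1 − 2 × 0.0194 = 96.12%.

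**Step 2: interim level.** With rho = 1, cumulative spending is alpha(t) = 0.025 × t. Setting this equal to 0.0125 gives t = 0.5, that is 10 of 20. The stated interim level is reproduced, as a share of the one-sided 0.025.

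**Step 3: final level.** The interim critical value for 0.0125 is c1 = 2.2414. The alpha left is 0.025 − 0.0125 = 0.0125. Solve P(Z1 < c1, Z2 > c2) = 0.0125 for a bivariate normal pair with correlation √0.5. The result is c2 = 2.125, a nominal one-sided level of 0.0168. The stated 0.0194 is not reproduced.

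Other readings do not give it either:

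- two-sided total of 0.025: 0.0161
- two-sided total of 0.05: 0.0336
- exact Pocock, equal levels: 0.0147 at each look
- t = 10/18 with rho = 1: 0.0139, then 0.0162

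Adding a binding futility boundary that spends beta 0.20 with rho = 1 at t = 0.5 gives drift 2.992, a stop for futility if z < 0.834, c2 = 2.0658 and a final level of 0.01942. That matches, but that this is the origin of the figure is an inference.

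**Step 4: overall one-sided error.** This is P(Z1 > c1) + P(Z1 < c1, Z2 > c2), with no futility stop.

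| Levels applied (interim, final) | t = 0.5 | t = 10/18 |
|---|---|---|
| 0.00625, 0.0097 (intervals as written) | 0.0140 | 0.0137 |
| 0.0125, 0.0194 (levels as written) | 0.0272 | 0.0267 |
| 0.0125, 0.0168 | 0.0250 | 0.0245 |

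A simulation of 8 million draws at t = 0.5 gave 0.0139, 0.0273 and 0.0250.

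**Step 5: the two rules in conflict.** Assume, for illustration, 40 independent interim observations with 38 captures. The exact one-sided p-value against 80% is P(X ≥ 38 | n = 40, p = 0.8) = 0.0079, below 0.0125, so the endpoint is met by the stated level. The Clopper-Pearson lower limit of the 98.75% interval is 79.4%, so it is not met by the stated interval. The 97.5% lower limit is 81.2%, so it is met.

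**Step 6: illustrative power.** Take an effect that has 80% power at a single one-sided 0.025 look (drift 1.96 + 0.8416) and t = 0.5. The chance of success at the interim is 30.3% with the 98.75% interval and 39.7% with the 97.5% interval. Overall power is 69.4% with the written intervals and 76.7% with levels 0.0125 and 0.0168. This is not the trial's own power, which depends on the number of observations and the within-patient correlation.

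**The case against.** The strongest reply is that Section 6 tells the analyst exactly which interval to compute and that this rule is safe. Its overall error is about 0.014 at half information and stays below 0.025 for every interim fraction from 0.3 to 0.8. Any success declared under it is valid on either reading. The interim is optional and the study is a small feasibility trial. All of this is true and limits the consequence to lost power and ambiguity. It does not remove the contradiction with Section 2. Reading 0.0125 and 0.0194 as two-sided contradicts the one-sided 0.025 and still gives 0.0161, not 0.0194, for the final level.

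A second reply is that 0.0194 can be reached without a futility boundary, if 0.0125 is spent at a true information fraction of about 0.69. That does not fit the stated function: with rho = 1 about 0.017 would be spent at that point (0.025 × 0.69 = 0.01725).

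Third, the 38-of-40 example is chosen to show the conflict. With 80 independent observations, both the 98.75% and the 97.5% exact intervals need 73 captures, and at the expected 97.5% success rate both pass with probability 99.9%. With 40 observations the pass probabilities are 74% and 92%. Capture is scored on every stimulated breath, so the two rules may well agree in practice. The plan does not allow one to say so in advance.

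Fourth, moving the interim interval from 98.75% to 97.5% relaxes a success criterion after the SAP has already described its cohort. This is a fair warning about how the correction is made, and the fix takes it up.

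**Conclusion.** The concern holds on both counts. The 98.75% and 98.06% intervals test at 0.00625 and 0.0097, half the levels the SAP pairs them with. The final level of 0.0194 cannot be derived from rho = 1 spending with success-only stopping, which gives 0.0168 at half information.

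The two errors pull in opposite directions. Used as written, the intervals leave a little under half of the 0.025 unspent. Correcting the intervals alone, to 97.5% and 96.12%, would raise the error to 0.0272. They must be corrected together.

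The step 1 conversion needs no assumption beyond the SAP's own convention. The overall error rates rest on a normal approximation and on t = 0.5, which the SAP does not state but which its 0.0125 implies. All of it applies only if the interim is done; otherwise the test runs correctly at 0.025.

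**What to change.** Amend the interim text in SAP Sections 2 and 6 together.

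- Delete 98.75% and 98.06%, and say that the levels are one-sided.
- Interim: one-sided 0.0125, lower limit of a 97.5% two-sided interval.
- Final: one-sided 0.0168, lower limit of a 96.64% two-sided interval (1 − 2 × 0.0168).
- State the information fraction. The pair above assumes 0.5 (10 of 20). It is also safe at 10 of 18, the most patients who can contribute bilateral data (total 0.0245). The exact levels for 10/18 are 0.0139 (97.22% interval) and 0.0162 (96.76% interval). If the interim holds less than half the information, the 0.0125 and 0.0168 pair slightly exceeds 0.025 (0.0255 at 0.45, 0.0259 at 0.40), so the final level should then be recalculated.
- Keep 0.0194, with a 96.12% interval, only if a binding futility boundary was intended. It must then be written in, replacing the statement that enrolment continues when the endpoints are not met.
- Date and justify the change, and say whether any capture results had been seen. If they had, the cautious alternative is to keep the written intervals, relabel the levels as one-sided 0.00625 and 0.0097, and drop the statement of how they were derived.

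The cost is SAP wording only, with no new data or patients. The price of the main correction is a final level of 0.0168 in place of the stated 0.0194.

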The PEPNS System Feasibility Study is being conducted to confirm the feasibility of phrenic nerve stimulation in the neck with PEPNS System to pace the diaphragm. The study will be used to confirm:

- The benefits of ultrasound imaging in guiding the deployment of the pacing leads across the phrenic nerve in the patient's neck;
- The ease of lead deployment in the neck;
- The current stimulation levels required to stimulate and contraction of the diaphragm in synchrony with the ventilator's inspiratory breaths; and
- Stability of stimulation thresholds as patients are repositioned (supine, recumbent, lateral).

The PEPNS technology consists of two disposable multipolar stimulation leads and an external function generator designed to stimulate the phrenic nerve in synchrony with the inspiratory cycle of the ventilator. The purpose being to exercise the diaphragm during positive pressure ventilation to minimize the reduction in diaphragmatic strength.

Beyond testing the feasibility of the technology in humans the purpose of the study is to also:

- Demonstrate that the human experience is consistent with the preclinical trial results.
- Collect preliminary data that may refine the most suitable patient population for a pivotal study.
- Characterize diaphragm thickness observed on patients using mechanical ventilation and phrenic nerve electrical stimulation if feasible.

Diaphragm stimulation parameters in terms of currents, current profile waveforms, voltages and charge density are similar to those used in chronic diaphragm pacing patients where ventilatory support is replaced with pacing. Subjects will be treated per the standard of care for patients on ventilatory support, with weaning trials conducted up to 48 hours where weaning criteria are met. Time to weaning from mechanical ventilation will be collected. Adverse events will also be collected and analyzed.

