2. ANALYSIS OBJECTIVES

The company informed the FDA of plans to conduct a First in Human feasibility study within an OUS Tier I country (Canada, Europe or Australia) and stated:

As part of this study the following would be evaluated

- a) Confirmation of the stimulation leads are easily deployed under ultrasound guidance
- b) Confirmation that the diaphragm is easily stimulated without collateral stimulation similar to the Taira publication in references.
- c) Confirmation of appropriate candidates for a pivotal study. Trending demonstrating that time to extubation is decreased when compared to historical data in similar patient population.

The first two patients enrolled in the trial will be analyzed specifically for safety of the procedure in terms of nerve damage which could result from electrical stimulation or mechanical damage due to lead insertion, patient movement or lead removal and any other adverse events. Compound motor action potential and nerve conduction time between the neck and diaphragm will be evaluated in the first two pilot patients. Since these patients are stimulated on the left phrenic nerve only, they will be included for the safety analysis only. The enrollment of subsequent patients was contingent upon these patients showing no damage to the phrenic nerve at ~30 days post stimulation in terms of the CMAP study, follow up x-ray and any reported adverse events deemed relevant to the procedure.

Primary and secondary endpoints for the study will be evaluated statistically in terms of per protocol (PP) and intent-to-treat (ITT) analysis. The clinical study protocol CIP0001 defined intent-to-treat as "All patients that were attempted to be treated with the PEPNS System but the procedure was aborted." The

	PEPNS Study Statistical Analysis Plan <small>CONFIDENTIAL: THIS DOCUMENT AND ALL INFORMATION CONTAINED HEREIN IS PROPRIETARY TO STIMDIA MEDICAL, INC. AND IS NOT TO BE DISCLOSED WITHOUT THE EXPRESS WRITTEN PERMISSION OF STIMDIA MEDICAL, INC.</small>	Document Number SAP0001	Rev. Level 1
---	--	-----------------------------------	------------------------

primary analysis will be per protocol and the secondary analysis will be intent-to-treat. Time of weaning from mechanical ventilation and diaphragm thickness from 0 to 48 hours will also be analyzed.

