3. ANALYSIS SETS/ POPULATIONS/SUBGROUPS

The only analysis populations that will be analyzed in this SAP are per protocol population as the primary analysis and intent-to-treat population as the secondary analysis. No other populations will be statistically analyzed since it is too small a data set to assess other subgroups.

There will be summary tables created for patient demographics. In general, summary statistics will include the mean, median, standard deviation, minimum and maximum for continuous measures and the number and frequency for categorical measures. This summary data will be reviewed to see if there are any trends that may have impacted study endpoints.

	PEPNS Study Statistical Analysis Plan <small>CONFIDENTIAL: THIS DOCUMENT AND ALL INFORMATION CONTAINED HEREIN IS PROPRIETARY TO STIMDIA MEDICAL, INC. AND IS NOT TO BE DISCLOSED WITHOUT THE EXPRESS WRITTEN PERMISSION OF STIMDIA MEDICAL, INC.</small>	Document Number SAP0001	Rev. Level 1
---	--	-----------------------------------	------------------------

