To see if the type of patient may have impacted the primary endpoint of diaphragm capture, the primary analysis will be rerun with type of patient added into the logistic regression as an independent predictor. A confidence interval will be constructed about the coefficient for type of patient and if that confidence interval overlaps zero then it will be assumed that the type of patient did not impact the primary endpoint.

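### SAP section 7 treats a confidence interval that includes zero as showing that patient type has no effect on capture, which about 10 patients cannot show

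*SAP*

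**What the plan says.** The last paragraph of SAP section 7 adds patient type to the primary logistic regression, which already has time point as a fixed effect and subject as a random effect. The decision rests on one interval, for the added coefficient: "if that confidence interval overlaps zero then it will be assumed that the type of patient did not impact the primary endpoint". The section gives no margin for a negligible effect, no power, no definition of the types, no number of patients per type and no interval level.

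The preceding paragraph of section 7 says that because the "study was very small no heterogeneity, multiplicity or confounder statistical analyses will be run". It then allows that "summary data may be presented for the different types of patients (neuro trauma, COPD etc".), so a by-type summary is optional, while the rerun and its conclusion are mandatory. SAP section 3 adds: "No other populations will be statistically analyzed since it is too small a data set to assess other subgroups".

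The question matters to the study. Protocol section 2 lists among its purposes: "Collect preliminary data that may refine the most suitable patient population for a pivotal study". SAP section 2 lists "Confirmation of appropriate candidates for a pivotal study", and SAP section 7 itself calls the comparison of patient populations a study objective.

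**The concern.** The rule turns a non-significant coefficient into a finding of no effect. To support no effect, the whole interval would have to lie inside a margin stated in advance. As written, the rule rewards imprecision: the fewer the patients and the wider the interval, the more surely it returns the reassuring answer.

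This study is exposed because patient type is a between-patient characteristic. Thousands of breaths per patient make each patient's own capture rate precise, but they add no patients. The SAP gives small size as its reason for running no heterogeneity analyses, and then specifies one with a firm negative conclusion.

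At stake is a sentence in the study report saying that patient type made no difference when the data were merely uninformative. It could mislead the choice of the pivotal population, although nothing in the documents ties that choice to this rule. The rerun cannot change whether the primary endpoint is met.

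**Working it through.** The plan states no power or error rate for this analysis, so there is no figure of its own to reproduce. The check asks how often the rule would conclude no effect when the types truly differ.

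**From the documents**
- 10 patients: SAP sections 7 and 8, and the ten patient IDs in SAP Table 3.
- Capture is scored for every stimulated breath (SAP section 11), with stimulation for up to 48 hours, so there are many breaths per patient.
- 97.5% and 90% are the expected rate and planning goal in the SAP sample size ("With an anticipated success rate of 97.5% and a performance goal of 90%, 80 observations would yield" at least 80% power). 80% is the goal actually tested.
- Two-sided 95% interval, taken from the primary analysis in SAP section 6.

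**Assumed, because the documents do not say**
- Two types, five patients each. For two types this is the most favourable split.
- Between-patient SD on the logit scale of 0.5, 1.0, 1.5 or 2.0.
- True rates of 97.5% versus 90%, 95% versus 85%, or 97.5% versus 80%, read as the rates for the median patient of each type.

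**Formulae**
- Difference d = logit(p1) − logit(p2). For 97.5% versus 90%: 3.664 − 2.197 = 1.466. For 95% versus 85%: 2.944 − 1.735 = 1.210. For 97.5% versus 80%: 3.664 − 1.386 = 2.277.
- With many breaths, SE = SD × √(1/5 + 1/5) = 0.632 × SD.
- The interval is the estimate ± 2.306 × SE (t, 8 df). The chance that it includes zero comes from the noncentral t with 8 df and noncentrality d/SE. At SD 1.0 and 97.5% versus 90%, d/SE = 1.466/0.632 = 2.32, and the chance is 47%.

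**Chance of wrongly concluding no effect (t interval, 5/5 split)**

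| True rates | SD 0.5 | SD 1.0 | SD 1.5 | SD 2.0 |
|---|---|---|---|---|
| 97.5% vs 90% | 2% | 47% | 72% | 82% |
| 95% vs 85% | 8% | 61% | 80% | 86% |
| 97.5% vs 80% | about 0% | 12% | 44% | 65% |

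**Other choices**
- Rates read as averages over patients: 2%/42%/65%/74% for the first row, 7%/55%/72%/79% for the second and 0%/7%/28%/43% for the third.
- Large-sample Wald interval (z = 1.96, maximum-likelihood variance, median-patient rates): under 1%/28%/55%/69% for the first row and 3%/42%/65%/74% for the second. That interval is too short with 10 patients. It amounts to a t cut-off of 1.96 × √(8/10) = 1.753 on 8 df, so it flags a difference 11.8% of the time when there is none.
- Wald interval with average rates, the most favourable combination, at SD 1.0: 24% for the first row and 36% for the second.
- Uneven split, first row, t interval, SD 1.0: 63% at 8/2 and 77% at 9/1.

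A Monte Carlo check of the first row at SD 1.0 (400,000 runs) gave 46.9% for the t interval and 28.4% for Wald.

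**What an interval including zero leaves open.** At SD 1.0 the t half-width is 2.306 × 0.632 = 1.458 logits, an odds-ratio factor of 4.3 either way. With one type at 97.5%, an interval centred exactly on zero reaches down to logit 3.664 − 1.458 = 2.206, about 90% capture in the other type. The rule would still report no effect.

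**The case against.** The best case against this point concerns its weight. The rerun is a supportive check in a single-arm feasibility study whose main methods are descriptive, and the worst outcome is one overstated sentence. The figures rest on an SD, a split and a true difference that the documents do not give. The 97.5% and 90% rates were not planned as rates for two patient types. If the true difference is 97.5% versus the tested goal of 80%, misses fall to 12% at SD 1.0. If patients are much alike (SD 0.5), a 5/5 split misses at most about 8%.

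All of that stands, and it limits what can be claimed about size. It does not rescue the rule. Even at 97.5% versus 80%, misses are 44% at SD 1.5, and at SD 1.0 they rise from 12% to about 29% with an 8/2 split or about 35% with a 98.75% interval.

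Three smaller objections have merit:
- The 95% level probably carries over from the primary analysis, since that analysis is rerun. However, SAP section 6 also sets 98.75% and 98.06% intervals if an interim analysis is done, so the level should be written down.
- The SAP section 3 sentence mainly explains the choice of analysis populations, although it does mention subgroups. The section 7 sentence is the stronger evidence.
- A factor with several types simply yields several coefficients. Even so, the rule as worded covers only one coefficient and one interval, and the examples suggest there may be more than two types.

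**Conclusion.** The concern holds. The inference is invalid whatever the numbers: an interval that includes zero does not establish no effect, and nothing elsewhere in the SAP or protocol softens the statement.

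How often it would mislead depends on the unknown between-patient spread, the split by type and the true difference. For 97.5% versus 90% or 95% versus 85% with a 5/5 split and SD 1.0, the rule misses the difference in 24% to 61% of studies, depending on the interval method and how the rates are read. Misses are rare only if patients are much alike or the true difference is large relative to their spread.

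This should be corrected, but it does not threaten the primary result.

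**What to change.** In SAP section 7:

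1. Delete the sentence that assumes no effect when the interval includes zero.
2. Define the patient types. State the interval level and method, including which level applies if an interim analysis is done.
3. Make the by-type summary mandatory: capture by type with the number of patients in each, and the estimated difference or differences with confidence intervals.
4. State that an interval including zero is inconclusive and that no conclusion of no effect will be drawn.
5. Reconcile this analysis with the statement in the same section that no heterogeneity or confounder analyses will be run.

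The cost is some rewording in one SAP section and one small table, with no new data. The report loses a reassuring statement that it could not have supported.
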